**Missing data**

Participants will be included in the analysis of the primary outcome irrespective of missing questionnaires as this is based on laboratory outcomes only. Participants with missing or inadequate blood samples on one of the sample days will be excluded from the antibody analysis.

For the secondary outcome (infection) which is based on self-reported information, participants are only under follow-up during the periods where they have completed follow-up questionnaires.

**Adverse events**

Adverse events will be described in terms of incidence in the randomization groups and more thoroughly presented in a table as part of supplementary material (Table 4). Serious adverse events (SAE) will be classified as related to study drugs (possible/probable/definite) or unrelated to study drugs (unlikely/doubtful). If related, they are classified as expected/unexpected (SAR/SUSAR).

**15.0 SUPPLEMENTARY INFORMATION**

**Figures and tables**

Figure 1: Flow chart, inclusion.

Figure 2: Study design.

Table 1: Baseline characteristics.

Table 2: Results primary outcome.

Table 3: Results infectious disease rate and association with influenza antibody level.

[figure not shown]
Figure 3: Results trained immunity.

Figure 4: Results lymphocyte response.

Table 4: Adverse events (AE) and Serious Adverse Events (SAE).

Table 5: Short description of Serious Adverse Events (SAE).

Figure 1: Flow chart, inclusion.

**Figure 2: Study design.**

A flow chart describing enrollment, follow-up visits, vaccinations, collection of blood samples, and surveys with a timeline.

**Table 1: Baseline characteristics.**

	Group 1	Group 2	Group 3	Group 4
Age, median (IQR)				
Sex female (%)				
Living alone (%)				
Spouse included in study (%)				
Active smoker (%)				
Previous smoker (%)				
Alcohol consumption, units per week, mean (SD)				
BMI, median (IQR)				
Chronic diseases				
Cardiovascular (%)				
Diabetes (%)				
Lung (%)				
Other (%)				
Level of education				
Low (%)				
Medium (%)				
High (%)				
Previously BCG vaccinated (%)				
Scar from BCG vaccination observed (%)				
COVID-19 vaccinated, yes (%) 				
One dose				
Two doses				
Three doses				

 COVID-19 vaccinated before enrollment.

**Table 2: Results primary outcome.**

Change in antibody levels to influenza virus strains included in the IIV, comparing levels at day 14 and day 42.

[figure not shown]
Influenza strain	Change in antibody titer from day 14 to day 42, mean (sd) $\beta$ (95% CI)			
	Group 1	Group 2 (Control)	Group 3	Group 4
A/Victoria	xx (xx-xx) xx (xx-xx)	xx (xx) (ref.)	xx (xx) xx (xx-xx)	xx (xx) xx (xx-xx)
A/Cambodia	xx (xx) xx (xx-xx)	xx (xx) (ref.)	xx (xx) xx (xx-xx)	xx (xx) xx (xx-xx)
B/Washington	xx (xx) xx (xx-xx)	xx (xx) (ref.)	xx (xx) xx (xx-xx)	xx (xx) xx (xx-xx)
B/Phuket	xx (xx) xx (xx-xx)	xx (xx) (ref.)	xx (xx) xx (xx-xx)	xx (xx) xx (xx-xx)
	Seroconversion N (%) OR (95% CI)			
A/Victoria	xx (%) x.xx(x.xx-x.xx)	xx (%) (ref.)	xx (%) x.xx (x.xx-x.xx)	xx (%) x.xx (x.xx-x.xx)
A/Cambodia	xx (%) x.xx(x.xx-x.xx)	xx (%) (ref.)	xx (%) x.xx (x.xx-x.xx)	xx (%) x.xx (x.xx-x.xx)
B/Washington	xx (%) x.xx(x.xx-x.xx)	xx (%) (ref.)	xx (%) x.xx (x.xx-x.xx)	xx (%) x.xx (x.xx-x.xx)
B/Phuket	xx (%) x.xx(x.xx-x.xx)	xx (%) (ref.)	xx (%) x.xx (x.xx-x.xx)	xx (%) x.xx (x.xx-x.xx)

**Table 3: Results infectious disease rate and association with influenza antibody level.**

Treatment group	Number (%)	Hazard ratio (95% CI)	Absolute risk reduction (95% CI)
Self-reported infection six months post-randomization			
Group 1	xx (x.x)	x.xx (x.xx–x.xx)	x.x% (x.x%–x.x%)
Group 2	xx (x.x)	x.xx (x.xx–x.xx)	x.x% (x.x%–x.x%)
Group 3	xx (x.x)	x.xx (x.xx–x.xx)	x.x% (x.x%–x.x%)
Group 4	xx (x.x)	x.xx (x.xx–x.xx)	x.x% (x.x%–x.x%)
Association between influenza antibody level at day 42 and infection rate during follow-up after day 42			
Antibody level by quartile	Number (%)	Hazard ratio (95% CI)	Absolute risk reduction (95% CI)
1 quartile	xx (x.x)	x.xx (x.xx–x.xx)	x.x% (x.x%–x.x%)
2 quartile	xx (x.x)	x.xx (x.xx–x.xx)	x.x% (x.x%–x.x%)
3 quartile	xx (x.x)	x.xx (x.xx–x.xx)	x.x% (x.x%–x.x%)
4 quartile	xx (x.x)	x.xx (x.xx–x.xx)	x.x% (x.x%–x.x%)

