### Objectives and hypothesis

We will test the effects of BCG vaccination on the specific immune response to IIV and on the immune system and health in general in people  $\geq 65$  years, with the aim to:

- Improve their specific antibody response to influenza vaccination.
- Improve their general resistance towards infections.
- Study the effect of BCG on classical lymphocyte-dependent responses, and the induction of innate immune memory.

We will test the following hypotheses:

- a) BCG vaccine given two weeks prior to, together with, or two weeks after IIV is associated with a 30% increase in seroconversion to IIV and/or a significant increase in influenza antibody titers.
- b) The hypothesized potentiating effects of BCG is due to a combination of classical lymphocyte-dependent responses, and the induction of innate immune memory (trained

immunity) in myeloid cells.

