## 10.0 STUDY METHODS

### Trial design

A single-blinded, placebo controlled, randomized clinical trial, with nested immunological studies. Participants are randomized 1:1:1:1 to four groups: BCG 14 days before, together with, or 14 days after IIV compared to placebo.

People  $\geq 65$  years of age who plan to accept the offer of seasonal influenza vaccination are eligible for participation.

Participants are vaccinated once at day 0 and twice at day 14 (one shot in each arm). All participants receive the standard seasonal IIV recommended by the Danish Board of Health. The participants will come back for a follow-up interview at day 42 and all are followed for six months post-randomization with electronic questionnaires about their health. These include information on symptoms and disease, potential side effects, other vaccinations, visits to general practitioner or on call doctor, and hospitalizations. Every survey period is 14 days, starting from day 0 (inclusion).

Blood samples for influenza antibody testing are collected from all participants at day 14 and 42. Samples for further immunological analyses are collected from subgroups at day 0, day 14, day 21, and day 42.

Vaccination schedule:

Group	Day 0 (one shot)	Day 14 (two shots)	Day 42
1	BCG	IIV + Placebo	Follow up visit
2 (Control)	Placebo	IIV + Placebo	Follow up visit
3	Placebo	IIV + BCG	Follow up visit
4	IIV	Placebo + BCG	Follow up visit

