### **Sample size**

We aim to include 75 participants in each group, 300 in total. With an anticipated seroconversion rate of 50% in the control group, we should be able to show a 30% increase in seroconversion rate associated with BCG vaccine with 80% power and an alpha of 0.05, anticipating 10% loss to follow-up.

All participants are followed for clinical symptoms for six months. With this sample size, we will only be able to show differences in clinical symptoms if such differences are pronounced.

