### **Exclusion/lost to follow-up**

Participants who are excluded after randomization or lost to follow up are not replaced.

Participants are under follow-up for six months post-randomization or until they withdraw their consent, migrate to another country, or die.

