### **Secondary outcomes**

*Self-reported infections:*

Infections are identified through information given by the participants in the electronic follow-up questionnaires, where they are asked to describe disease episodes every 14 days. They are asked if they have been ill, and then asked to cross off their symptoms on a list. Furthermore, we ask them to provide the most likely cause for their illness. Disease episodes are characterized as infections if participants report symptoms compatible with an infectious disease or they report an infectious disease diagnose as the cause of their illness. Criteria for self-reported infection:

- Having one or more of the following symptoms: fever, cough, sore throat, runny nose/nasal congestion (common cold symptoms), loss of smell or taste sense, vomiting, or diarrhea with or without general symptoms such as headache, myalgia, dysarthria, or fatigue.
- Having dyspnea AND fever with or without general symptoms such as headache, myalgia, dysarthria, or fatigue.
- Having described an infectious disease as the self-estimated cause of illness. This is a free-text field and participants answers will be classified as infectious disease or not by medically trained study personnel.

Baseline for analysis is set at day 14 reflecting completion of the allocated vaccinations. We will however also conduct the analysis from day 0-14. Participants can register a maximum of one infectious disease event per survey period (14 days).

A secondary analysis of association between influenza antibody level and subsequent risk of infection will be performed to test if high antibody titers correlate with risk of infection.

*Immunological outcomes (subgroup analyses):*

A random subset of participants (the first to accept) have extra blood samples taken for further immunological analyses.

1. Lymphocyte-dependent responses 7 days after influenza vaccination
2. The induction of innate immune memory 14- and 42-days post-randomization

For the lymphocyte analyses, 10 participants from groups 1-3 will have blood drawn on day 21, exactly 7 days after influenza vaccination. We will assess the effect of the different treatment combinations on the response to the influenza vaccine, examining activated

influenza antibody-secreting B-lymphocytes. Due to the different timing of the influenza vaccination, participants from group 4 are not part of this analysis.

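### Part B names no contrast for infections and plans no overall estimate of the BCG effect, although general resistance to infection is one of its aims

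*SAP*

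**What the plan says.** All references are to Part B of the SAP.

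- **Aim.** Section 2.0, Objectives and hypothesis, lists as a separate aim: "Improve their general resistance towards infections". BCG timing relative to the inactivated influenza vaccine (IIV) enters only in hypothesis (a), which concerns seroconversion and titers.
- **Design.** Section 10.0, Trial design: "Participants are randomized 1:1:1:1 to four groups: BCG 14 days before, together with, or 14 days after IIV compared to placebo". In the schedule, Group 1 has BCG on day 0, Groups 3 and 4 have it on day 14, and Group 2 never has it. IIV is given on day 14 in Groups 1, 2 and 3, and on day 0 in Group 4.
- **Start of the infection analysis.** Section 13.0, Secondary outcomes: "Baseline for analysis is set at day 14 reflecting completion of the allocated vaccinations". A separate analysis of days 0 to 14 is also planned.
- **Follow-up.** Section 12.0: "Participants are under follow-up for six months post-randomization".
- **Model.** Section 14.0 specifies an Andersen-Gill Cox model for recurrent infections. It does not say which groups are compared.
- **Reporting.** In the Table 3 block "Self-reported infection six months post-randomization", Groups 1 to 4 each have a row with a hazard ratio cell, Group 2 included. No reference is marked. The antibody table (Table 2), by contrast, marks Group 2 as control and reference.
- **Power.** Section 10.0, Sample size, says of clinical outcomes: "we will only be able to show differences in clinical symptoms if such differences are pronounced".

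**The concern.** The infection aim is about BCG itself, and the analysis starts at the point when every participant in the three active groups should have received it. A reader of the results will want one answer: did BCG lower the infection rate compared with no BCG? Neither the methods text nor the table shell provides for that estimate.

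If the shell is followed with Group 2 as reference, the aim is addressed by three hazard ratios, each using one third of the BCG recipients. Nothing says how to read them together. If one group differs from control and two do not, the plan does not say whether the aim was met. With three comparisons against a shared control, each at the two-sided 5% level, the chance of at least one nominally significant result under the null is about 12.5% (equal information per arm, pairwise correlation 0.5).

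**Working it through.** **The plan's own figure.** The SAP gives no power or event rate for infections in Part B, so there is no figure to reproduce on this point. The group size comes from the seroconversion calculation: "We aim to include 75 participants in each group, 300 in total". That calculation is a separate matter and is not used here beyond the group size.

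**Who has had what by the day 14 baseline** (schedule, section 10.0):

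| Group | BCG | IIV |
|---|---|---|
| 1 | day 0 | day 14 |
| 2 (control) | never | day 14 |
| 3 | day 14 | day 14 |
| 4 | day 14 | day 0 |

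From day 14, Groups 1+3+4 (target 3 × 75 = 225) versus Group 2 (target 75) is a randomized contrast of any BCG against none. Groups 1+3 (150) versus Group 2 (75) is the same contrast with IIV timing matched. In the day 0 to 14 analysis only Group 1 has had BCG, so pooling does not apply there.

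**Precision.** Let *e* be the number of events per arm, about equal across arms near the null, with no over-dispersion. For *k* BCG arms against control:

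SE(log HR) = √(1/e + 1/(k·e))

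- k = 1: √(2/e)
- k = 2: √(1.5/e); ratio to one arm √(1.5/2) = 0.866, a 13% reduction
- k = 3: √(1.333/e); ratio √(1.333/2) = 0.816, an 18% reduction, or 1.5 times the information

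These ratios do not depend on *e*.

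**Power and detectable effect.** The infection rate is not in the SAP, so *e* = 30, 60 and 90 are assumptions. The hazard ratio of 0.75 is borrowed from the 25% reduction hypothesized in Part A. Power = Φ(0.2877/SE − 1.96). The hazard ratio detectable with 80% power = exp(−(1.96 + 0.8416)·SE).

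| Events per arm | Contrast | SE | Power at HR 0.75 | Detectable HR |
|---|---|---|---|---|
| 30 | one arm vs 2 | 0.258 | 20% | 0.49 |
| 30 | 1+3 vs 2 | 0.224 | 25% | 0.53 |
| 30 | 1+3+4 vs 2 | 0.211 | 28% | 0.55 |
| 60 | one arm vs 2 | 0.183 | 35% | 0.60 |
| 60 | 1+3 vs 2 | 0.158 | 44% | 0.64 |
| 60 | 1+3+4 vs 2 | 0.149 | 49% | 0.66 |
| 90 | one arm vs 2 | 0.149 | 49% | 0.66 |
| 90 | 1+3 vs 2 | 0.129 | 61% | 0.70 |
| 90 | 1+3+4 vs 2 | 0.122 | 66% | 0.71 |

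**Check under other assumptions.** Take 67.5 evaluable per arm (75 less 10%), *L* events per control participant, fewer events in the BCG arms under the alternative, and over-dispersion φ: variance = φ·[1/(67.5·L) + 1/(k·67.5·L·0.75)]. For L = 0.5, 1.0 and 2.0, power at HR 0.75 moves from one arm to the 1+3+4 pool as follows:

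- φ = 1: 19% to 29%, 34% to 50%, 59% to 79%
- φ = 1.5: 14% to 21%, 24% to 36%, 43% to 62%

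The direction and size of the gain agree. Power stays below 80% in every case tried.

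**The case against.** **The arm-by-arm reading is inferred.** Section 14.0 is silent and Table 3 is only a shell. A reader might infer that the plan commits to three separate comparisons of 75 with 75 and excludes a combined one. The documents do not say that. What stands is narrower: no contrast or reference is named, and no overall estimate is planned.

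**Reporting by randomized arm is a legitimate default.** Part B is built around timing, neither of its two lettered hypotheses concerns infection, and infection is a secondary outcome whose low power is admitted. Part A compares BCG with placebo for infection in 1706 participants. This lowers the stakes. It does not supply an estimate for an aim that Part B sets itself.

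**The pool is not clean.** A reader might infer that from day 14 the trial is simply BCG against placebo, 225 to 75. The schedule does not support that. Group 4 had IIV 14 days before control did, so a third of the pool differs from control in IIV timing as well as BCG. Groups 3 and 4 receive BCG on the baseline day, while Group 1 is already 14 days past it. Fever alone meets the infection criteria in section 13.0 and is also a listed adverse event in Table 4, so early vaccine reactions may be counted as infections, unevenly across the groups. These objections stand. They call for a stated qualification and a sensitivity contrast, and they do not remove the case for an overall estimate. Matching on IIV timing (Groups 1+3) does not settle the fever question, because Group 3 also has BCG at baseline.

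**The extra row does not remove multiplicity.** Correct: the three group rows remain. The gain is that one contrast is named in advance as the answer to the aim.

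**Conclusion.** The point holds as a gap in specification. Part B states an infection aim, names no contrast for it, marks no reference group and plans no overall BCG estimate, although the schedule and the chosen baseline make one available from day 14.

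Compared with a single arm against control, the gain in precision is about 18% in the standard error for Groups 1+3+4 and about 13% for Groups 1+3, near the null and without over-dispersion. The power figures rest on assumed event counts and a hazard ratio taken from Part A. It would go too far to say that pooling gives the infection aim adequate power: over the assumed range it does not, and the SAP's own caveat stands. The consequence is moderate, since this is a secondary outcome, but the change is cheap and should be made.

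**What to change.** In section 14.0 and Table 3 of Part B:

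1. Name Group 2 as the reference for the infection hazard ratios.
2. Prespecify any BCG (Groups 1+3+4) versus placebo (Group 2), from day 14, as the overall infection contrast in the same Andersen-Gill framework, with its own row in Table 3.
3. Keep the three group-specific hazard ratios as secondary rows.
4. State that Group 4 received IIV 14 days earlier than control, and add Groups 1+3 versus Group 2 as a sensitivity contrast with IIV timing matched.
5. Note that fever soon after vaccination in Groups 3 and 4 may count as infection.
6. Limit the pooling to follow-up from day 14, and say so in the row label.

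The cost is two additional model fits, two table rows and a few sentences. No new data are needed and no planned result is lost. The drawback is that the pooled estimate averages over BCG and IIV timing; the retained group rows still show the separate estimates.

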### Figure 3: Results trained immunity.

Boxplots showing fold increase in cytokine production after stimulation with bacterial antigens and influenza vaccine at day 0, day 14, and day 42 for each treatment group.

\* Denotes within-group statistically significant change in cytokine levels between day 0 and 14 or between day 14 and 42

Δ Denotes between group statistically significant different change in cytokine levels between day 0 and 14 or between day 14 and 42

**Figure 4: Results lymphocyte response.**

Graphs showing numbers and or percentage of activated B-lymphocytes at day 21 per treatment group.

**Table 4: Adverse events (AE) and Serious Adverse Events (SAE).**

Endpoint	Treatment group			
	1	2	3	4
	Number (%) [M/F]			
Any SAE				
Hospitalization for any reason				
Death due to any reason				
Injection site reaction				
Minor abscess/wound				
Severe local reaction (abscess)				
Fever				
Fatigue				
Headache				
Lymphadenitis				
Blood or lymphatic disorder				
Cardiac disorders				
Endocrine disorders				
Gastrointestinal disorders				
Infection				
Musculoskeletal and connective tissue disorders				
Nervous system disorders				
Respiratory disorders				
Urological and gynecological disorders				

Unknown/other				
Life threatening				
Required/prolonged hospitalization				
Resulted in death				

**Table 5 Short description of Serious Adverse Events (SAE)**

No	Category	Outcome	Description	Group 	Sex	Week 	Before/after 
1							
2							
3							
4							
5							
6							
7							
8							
9							
10							

Randomisation group.Weeks after inclusion.Occurrence before or after other vaccines were administered to the participant.

